4. STUDY DESIGN AND METHODOLOGY

Specific Aims and Hypotheses

Specific Aim 1: To test effects of GLP1RA on hypothalamic obesity prospectively. *We hypothesize that treatment with GLP1RA will significantly reduce adiposity in patients with HO. We furthermore hypothesize that GLP1RA treatment will lead to increased satiety.* To this end, we propose to conduct a double blind, placebo-controlled, randomized trial of once weekly extended release exenatide (ExQW) on metabolic and clinical outcomes. Following baseline testing, 48 patients (10-25y at time of enrollment) with HO will be randomly assigned with equal allocation to ExQW or matching placebo injection for 36 weeks, followed by an 18-week open label extension during which all patients will receive ExQW. Our primary endpoint is percent change in BMI after 36 weeks. Secondary endpoints will include changes in body fat, and satiety by free buffet meal test.

Specific Aim 2: To determine effects of GLP1RA on cardiometabolic risk factors. *We hypothesize that GLP1RA will also lead to (1) favorable changes in blood glucose, lipid profile, and inflammatory marker, and (2) reduced insulin secretion during an oral glucose tolerance test.* In the same cohort, we will examine changes in blood glucose, lipid profile, inflammatory markers, and insulin resistance by testing insulin secretion during an oral glucose tolerance test after adjustment for glucose response and adiposity.

Specific Aim 3: To explore additional outcome measures, and predictors of treatment responses. HO represents a disorder of energy homeostasis.

Aim 3 A: *To test the hypothesis that GLP1RA will normalize homeostasis by increasing EE in relation to energy intake.* This and prior hypotheses allow us to test potential predictors of treatment outcomes.

Aim 3 B: *To test the hypotheses that (1) a lower hypothalamic lesion score and (2) lower fasting serum leptin as well as (3) higher pretreatment hyperphagia will be associated with better BMI outcomes.*

The study will include brain lesion scoring, behavioral and hormonal measures, free-living total daily energy expenditure by doubly labeled water (DLW), energy intake by 24h dietary recall, and activity by actigraphy.

Overview/Scope

Study Design

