reacts 100% with amidated and acylated α -MSH and 79% with des-acylated α -MSH). The leptin to adiponectin ratio provides information regarding the risk of metabolic syndrome.⁹⁰⁻⁹³ All endocrine measures will be performed at the PI's lab at Seattle Children's Research Institute. In our laboratory, intra-assay coefficients of variation (CV) are <8%, and inter-assay CVs are <10% for these methods. For all assays, all samples will be run in duplicate.

OGTT derived measures. The assessment of dynamic changes of glucose and insulin secretion has clear advantages over static tests such as fasting insulin and glucose levels. Calculation models have been established for using OGTT insulin and glucose data to calculate first and second phase insulin secretion that correlate well with clamp data, and give surrogates for β -cell function and insulin sensitivity.⁹⁴⁻⁹⁷ In our study, we will assess insulin sensitivity by whole body insulin sensitivity index (WBISI) that encompasses both hepatic and peripheral tissue insulin sensitivity.⁹⁸ As exploratory outcome parameters, the first phase insulin response to oral glucose will be calculated by insulinogenic index (IGI), which is a surrogate of the β -cell function,⁹⁵ using the formula: $IGI = (Ins_{30\ min} - Ins_{0\ min}) / (Gluc_{30\ min} - Gluc_{0\ min})$.⁹⁴ Insulin resistance will be also estimated by homeostasis model assessment of insulin resistance (HOMA-IR).⁹⁹ Change in glucose metabolism parameters will be adjusted to Δ BMI.

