Treatment dosage and duration are based on prescribing information and prior successful clinical trial weight loss results.^{31,110} The placebo-control group is an essential arm in this trial as study measures can change over time without drug intervention and it supports the evaluation of efficacy and safety. The drug and placebo kits will be supplied by AstraZeneca, or the current pharmacologic company responsible for ExQW. Exenatide vials or pens 2.0 mg powder for injection will be supplied. All subjects will have weekly phone calls when not coming for a study visit, to check adherence and any potential

adverse effects. Any evidence for adverse effects will be discussed with the PI of each site and safety clinical visits will be considered.

All study medication will be stored/locked in the investigational pharmacy under appropriate temperature conditions. Dispensing and accountability records will be maintained by appropriate staff members.

Analysis

Analysis plan and sample size calculations by Aim.

The research team includes personnel with statistical and data management expertise for overseeing data collection, storage methods, and the following analyses (see letter of support, [name]). Adherence data collected during the placebo run-in phase will be summarized descriptively. All subjects completing the run-in phase will go on to the randomized treatment phase. The primary analyses will use the intention-to-treat (ITT) approach; i.e., subjects will be analyzed according to their randomized assignment regardless of treatment received. In addition, data of all completers will be analyzed separately as a sensitivity analysis. While every attempt will be made to collect complete data and retain all subjects, all sample size and power calculations account for dropout. Statistical methods have been selected to allow for inclusion of partial data. All testing is two-sided and $\alpha=0.05$. Repeated measures analyses will be conducted using SAS (SAS Institute, Inc., Cary, NC, USA) or R (The R Foundation for

Statistical Computing).

Analysis populations: All eligible subjects randomized will be included in the ITT population. The ITT population will be the primary analysis population for all primary, secondary, and tertiary outcomes. The safety population will be the primary population for all safety analyses, and include all subjects who receive at least one dose of study drug or placebo.

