Aim 2: To determine effects of GLP1RA on cardiometabolic risk factors. Secondary outcomes analysis: Secondary outcomes are change in the following metabolic CVD risk factors: blood glucose, triglycerides, HDL cholesterol, and hsCRP. All continuous secondary efficacy endpoints will be analyzed using similar repeated measures analyses to those previously described for the primary outcome to examine differences in the change in secondary outcomes, one at time, from baseline to 36 wk. Histograms will be examined, and if data are markedly skewed right, log transformations will be applied prior to analysis. Measures of insulin resistance and insulin secretion will be compared from baseline to 18 and 36 wk to test whether treatment effects are beneficial during the second half of intervention. Sample size and power: Table 3 shows observed relative effect sizes in our preliminary study for between treatment comparison of change from baseline to 3 mo (dataset from previous study²²). Assuming a normal distribution of changes, a type I error rate of 0.05, and dropout rate of up to 20%, a sample size of 24 subjects per group (19 evaluable) will provide 85% power to detect relative treatment effect sizes of 1 or greater (in absolute value) for changes in cardiometabolic risk factors in patients with HO, which is consistent with the preliminary study.

Expected results and benchmarks for success (secondary efficacy endpoints): We expect that GLP1RA treatment will lead to improved metabolic CVD risk factors (higher HDL; lower blood pressure, blood glucose, hsCRP, and triglycerides).

Aim 3: To explore additional outcome measures, and predictors of treatment responses.

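### The plan adjusts glucose-metabolism changes for BMI change, an outcome of treatment, while the Aim 2 model for blood glucose omits it, and nothing says which analysis is the main one

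*Combined protocol and SAP*

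**What the plan says.** All references are to section 4 of the combined protocol and SAP.

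- **Study Measures, OGTT derived measures.** After introducing WBISI, IGI (called exploratory) and HOMA-IR, the paragraph ends: "Change in glucose metabolism parameters will be adjusted to" ΔBMI. It does not label this adjustment supportive or limit it to particular parameters.
- **Analysis, Aim 2, Secondary outcomes analysis.** Blood glucose is named as a secondary outcome, with triglycerides, HDL and hsCRP. "All continuous secondary efficacy endpoints will be analyzed using similar repeated measures analyses to those previously described for the primary outcome". Insulin resistance and secretion are only said to be compared from baseline to 18 and 36 weeks.
- **Analysis, Aim 1, Primary outcome analysis.** The covariates of the model being borrowed are the stratification variables: site, age and gender. BMI change is the outcome there.
- **Table 1.** OGTT glucose at 0 and 120 minutes is an Aim 2 secondary outcome. HOMA-IR and WBISI are Aim 3 tertiary outcomes and predictors.
- **Specific Aim 2.** The plan will examine "insulin resistance by testing insulin secretion during an oral glucose tolerance test after adjustment for glucose response and adiposity". It does not say whether adiposity means the baseline value or the change.
- **Aim 2, Sample size and power.** The claim is that "a sample size of 24 subjects per group (19 evaluable) will provide 85% power". The target is a standardised between-arm difference of at least 1 SD, and it is set for the Aim 2 risk factors as a group.

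**The concern.** Percent change in BMI is the primary endpoint, and the plan expects the drug to lower it. Adjusting the glucose result for BMI change therefore conditions on something treatment has altered after randomisation. The adjusted contrast then targets the part of the drug effect that does not act through BMI. Even that reading needs an assumption that randomisation does not secure: that nothing else drives both BMI change and glucose change. Aim 2 hypothesises that the drug improves glucose, which is a total effect.

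The plan thus offers two models, answering different questions, for what may be the same secondary endpoint. An analyst could defend either one after seeing the data. The Aim 2 power statement describes only the unadjusted comparison.

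**Working it through.** **Inputs from the documents.** Equal allocation; 24 per arm with 19 evaluable; α = 0.05 ("All testing is two-sided"); powered effect 1 SD. Table 3 gives the preliminary between-arm difference in BMI change as −4.29/3.84 = −1.12 SD (percent) and −1.74/1.25 = −1.39 SD (absolute). Both are used, because the adjustment sentence says ΔBMI while the primary endpoint is the percent change.

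**Input not in the documents.** ρ, the within-arm correlation between BMI change and the glycaemic change, with both coded so that positive means benefit. It is assumed and varied. The 3-month BMI differences in Table 3 are also assumed to apply at 36 weeks.

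**Step 1: the plan's own figure.** Two-sample t test, noncentrality = 1 × √(19/2) = 3.08, 36 df: power **85.1%**. The stated 85% reproduces for the unadjusted comparison.

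**Step 2: add BMI change as a covariate.** With d the between-arm BMI difference in SD units:

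- adjusted effect = 1 − ρd
- residual SD = √(1 − ρ²)
- variance inflation = 1 + d²/4, which is 1.31 for d = 1.12 and 1.48 for d = 1.39
- noncentrality = [(1 − ρd)/√(1 − ρ²)] × √(19/2)/√(variance inflation), with 35 df

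Worked case, d = 1.12 and ρ = 0.3: effect = 1 − 0.336 = 0.664; divided by √0.91 = 0.954 this is 0.696; noncentrality = 0.696 × 3.08/√1.3136 = 1.87; power 44%.

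| ρ | Effect, d = 1.12 | Power | Effect, d = 1.39 | Power |
|---|---|---|---|---|
| −0.2 | 1.22 | 90% | 1.28 | 89% |
| 0 | 1.00 | 74% | 1.00 | 69% |
| 0.2 | 0.78 | 54% | 0.72 | 44% |
| 0.3 | 0.66 | 44% | 0.58 | 32% |
| 0.4 | 0.55 | 35% | 0.44 | 22% |
| 0.5 | 0.44 | 26% | 0.31 | 14% |

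A simulation of 20,000 trials at d = 1.12 gave 73%, 43% and 26% for ρ = 0, 0.3 and 0.5, within two points of the formula.

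**Step 3: read the table.** Two mechanisms are at work. At ρ = 0 the effect is unchanged, and power falls only because treatment arm and BMI change are collinear. Shrinkage of the effect requires ρ > 0. A negative ρ of sufficient size raises both effect and power.

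**The case against.** The strongest reply concerns scope. The sentence closes a paragraph on derived indices, which the plan ranks as exploratory or tertiary. Glucose at 0 and 120 minutes is introduced in the preceding paragraph, Metabolic outcomes, with no adjustment stated. The Aim 2 analysis text names no BMI covariate, whereas Aim 3a writes BMI change into its energy-expenditure ANCOVA explicitly. On that narrow reading no secondary glucose endpoint is affected. This is a fair reading, but not the only one: the wording is not confined to the indices, the paragraph heading refers to OGTT measures, and Table 1 takes the secondary glucose outcome from the OGTT. The reach to secondary glucose is probable, not certain. Even read narrowly, the indices themselves would be adjusted for an outcome of treatment.

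Three stronger readings are tempting and are not supported.

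- *That the glycaemic effect and the power are necessarily cut.* The size and direction depend on ρ, which the documents do not give.
- *That a drug working wholly through weight loss would be reported as having no glycaemic effect.* No text makes the adjusted result the only or main one. In the linear working above, an adjusted effect of zero from a true 1 SD also needs ρ = 1/1.12 = 0.89, or 1/1.39 = 0.72 on absolute BMI.
- *That the insulin analysis contradicts the Aim 2 analysis section.* Specific Aim 2 openly declares adjustment for glucose response and adiposity, and the analysis section says only that the insulin measures will be compared. Insulin secretion relative to glucose is a declared target quantity, so removing glucose response would replace it. What is missing is whether adiposity is the baseline value or the change.

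**Conclusion.** The point holds as an unresolved conflict over the main analysis. It is firmest for the derived indices, where the adjustment sentence plainly applies, and probable for secondary OGTT glucose, where two models compete. For any parameter covered, the BMI-adjusted contrast does not estimate the total effect hypothesised in Aim 2 and is open to confounding of BMI change with glucose change.

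The 85% power is correct for the unadjusted comparison and was not computed for the adjusted one. The adjusted figures above are illustrative: they rest on an assumed ρ, a linear model, a true effect of 1 SD, and 3-month BMI differences carried forward to 36 weeks. The primary endpoint, HDL, triglycerides and hsCRP are untouched, so the 85% still stands for those three risk factors. This should be settled before unblinding.

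**What to change.** 1. In the Aim 2 analysis text, state that the main analysis of glucose (0 and 120 minutes) and of change in the OGTT-derived indices is the primary-type model with site, age and gender, and without BMI change or adiposity change.
2. Under OGTT derived measures, restrict the ΔBMI sentence to a labelled exploratory weight-independent analysis, reported beside the main estimate with its no-confounding assumption stated.
3. For insulin secretion in Specific Aim 2, keep the declared adjustment for glucose response. Specify that adiposity in the main analysis is the baseline value, and show any adjustment for change in adiposity as supportive.
4. Note that the Aim 2 power refers to the unadjusted comparison.

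The cost is a few sentences and one extra table column, with no new data. The weight-independent question is kept.

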Table 1. Summary of Study Measures and Outcomes and Their Use in the Proposed Research

Measure	Domain	Instrument	Aim	Role/Application
$\Delta\text{BMI}\%$	Adiposity	Anthropometry	1	Primary outcome
Total body fat mass	Body composition	DEXA	1	Secondary outcome
Fat and total calorie intake	Post test meal satiety assessment	Free buffet meal analysis	1	Secondary outcome
Glucose tolerance	Glucose tolerance, MetS	Glucose at 0', 120' (OGTT)	2	Secondary outcome
HDL, triglycerides	MetS	Fasting lipids	2	Secondary outcome
hsCRP	Inflammation	hsCRP at fasting time point	2	Secondary outcome
Free living EE	Energy homeostasis	Doubly labeled water	3	Tertiary outcome
Energy intake	Energy intake	24h dietary recall (ASA24)	3	Tertiary outcome
Leptin, adiponectin, sOB-R, α -MSH, HOMA-IR, WBISI	Energy homeostasis, leptin sensitivity, and insulin resistance	Baseline and stimulated hormones	3	Tertiary outcomes and predictors

Aim 1: To test effects of GLP1RA on hypothalamic obesity prospectively.

Sample: Available anthropometry measures will be included in the analyses (see also Fig. 1 below).

Primary outcome analysis: For efficacy analysis the primary outcome is % change in BMI from week 0 (baseline) to 36 wk. A piecewise (separating the randomized and run out phases) linear mixed-effects model¹¹¹ will be fit with % change in BMI from baseline to 36 wk as the outcome; treatment, time, and the interaction between treatment and time as factors of interest; and randomization stratification variables (site, age, and gender) included as covariates. This model is a generalization of analysis of covariance (ANCOVA) that allows all follow-up repeated measures to be included.

Table 2. Additional Descriptive Parameters, Predictors and Covariates used in Study

Measure	Domain	Instrument	Aim
ΔBMI , ΔBMI z-score	Adiposity	Anthropometry	1
Subjective appetite	Hunger and fullness rating	Visual analog scale	1
Syst. & diast. BP	CVD risk factor, MetS	Ambulatory BP	2
Exercise	Physical activity measure	Actigraphy ^{112,113}	3
Energy intake	Energy intake	24h dietary recall	3
Eating behavior	Assessment of overeating and food reward	Overeating (CEBQ), ⁷⁶ & hyperphagia. ⁷⁷	3
Brain lesion score, hypothalamic region and residual lesion volumes	Structural lesion in the pituitary-hypothalamic area	Brain MRI images	3

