between treatment and time will be used to specifically test for a significant difference in % change in BMI from baseline to 36 wk post-treatment and 54 wk (end of open label extension). Additionally, descriptive summaries will be prepared for change in BMI z-score to supplement interpretation of findings. Study outcomes, their use, and descriptive parameters are in Tables 1 & 2.

Table 3 Aim	Outcome	Observed Δ Exenatide vs. Control	Observed pooled Std. Dev.	Observed relative effect size
1	% ΔBMI	-4.29	3.84	-1.12
1	Absolute ΔBMI	-1.74	1.25	-1.39
2	$\Delta\text{Glucose AUC}$ (per 100)	-29.36	26.44	-1.11
2	$\Delta\text{Insulin}$ (mU/L)	-7.62	7.14	-1.07

Sample size and power: Table 3 shows observed relative effect sizes in our preliminary study for the between-treatment comparison of change from baseline to 3 mo (data from previous study²²). Assuming a normal distribution of changes, a type I error rate of 0.05, and a dropout rate of up to 20%, a sample size of 24 subjects per group (19 evaluable) will provide 85% power to detect relative treatment effect sizes of 1 or greater (in absolute value) for % change in BMI, which is consistent with the preliminary data.

Expected result: We expect GLP1RA treatment will reduce BMI (primary efficacy endpoint). Further we expect that GLP1RA treatment will reduce total body fat mass and increase satiety (assessed by hunger VAS as well as fat and total calorie intake at free buffet test meal).

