5. SUBJECTS

Subjects

It is anticipated approximately 16 participants will be treated per year (5-6 per study site) during the first three years of the study. We expect to screen 80 subjects to get 48 subjects enrolled and 38 to complete the study (potential dropout rate of rate of 20%). Subjects will be between the ages of 10-25 y old at time of enrollment (11-27 y at end of intervention), and we expect each patient to complete the 56 week study.

Recruitment

We will recruit patients from the endocrinology clinics at the three sites, and will accept referrals from other endocrine providers. We will be advertising the study to other Pediatric Endocrinologists through a secure message board.

Enrollment

The PI at each site will screen and consent/assent subject or designate other qualified study staff to do so. Qualified participants will start with a 2-week placebo run-in to test adherence to the protocol. Immediately afterwards, subjects will be assigned treatment using a permuted-block randomization (1:1) with varying block sizes constructed by the Children's Core for Biomedical Statistics (CCBS) of Seattle Children's Research Institute (SCRI) stratified by study site, two age groups (10-14y, 15-25y), and gender. This is a double-blind study (participants and investigators both blinded). The study statistician will be blinded as well; a second statistician not involved in the conduct of the study will be responsible for the final preparation of the randomization scheme. Only the independent CCBS statistician and dispensing pharmacy at each site will know assigned study medications. It is anticipated approximately 16 participants will be treated per year (5-6 per study site) during the first three years of the study. We expect to screen 80 subjects to get 48 subjects enrolled and 38 to complete the study (potential dropout rate of rate of 20%). As we would expect many of these participants to be prepubertal as they have hypogonadotropic hypogonadism by virtue of their disease, pubertal status will not be used as an inclusion or exclusion criteria for the study.

Inclusion Criteria

- Age 10-25 years at time of enrollment
- Diagnosis of hypothalamic obesity with age- and sex adjusted BMI $\geq 95\%$ or BMI $\geq 30 \text{ kg/m}^2$ if over 18 y
- History of craniopharyngioma or another tumor located in the hypothalamic area
- Hypothalamic lesion documented by neuroradiology
- ≥ 6 months post-surgical or radiation treatment

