Study Visits (SVs): After the initial screening visit, there will be 5 study visits (see overview and measures in **Fig. 1**) to assess adherence, drug safety, outcomes, and to distribute the drug or placebo. Hypoglycemia medications will be adjusted as needed. During the duration of the treatment, subjects with persistent abdominal pain and nausea/vomiting will discontinue study medication and be evaluated for acute pancreatitis and cholecystitis. In children, most adverse effects are mild GI effects that are transient.¹¹⁷ Subjects not tolerating their current dose will be discontinued from study at PI's discretion. Study medication will resume if and only if no significant adverse event is found and subjects concur. Subjects need to fast and refrain from exercise for ten hours prior to study visits for fasting blood draws. Physical exams including Tanner staging, and inspection of injection sites will be done at all visits (except no Tanner staging at 6 weeks visit). If a subject withdraws from the study or is withdrawn by an investigator for any reason, subjects will be asked to complete SV4 study procedures, not including the DEXA scan.

Other measures assessed at SVs (see Fig. 1):

- Questionnaires (eating, activity): SVs 1, 3, 4,
- 24h dietary recall-done the week prior to : SVs 1, 3, 4, 5
- Anthropometry: SVs 1, 2, 3, 4, 5
- Vital signs: SVs 1, 2, 3, 4, 5
- Actimetry: SVs 1, 3, 4
- Blood for metabolic outcomes: SVs 1, 3, 4, 5
- OGTT: SVs 1, 3, 4
- Energy intake at free buffet meal: SVs 1, 4
- Whole body DEXA in order to evaluate body composition: SVs 1, 4
- DLW energy balance assessment: SVs 1, 4
- ECGs: SVs 1, 3, 4, and 5
- Safety labs (electrolytes, CBC, lipase, amylase, glucose, ALT, AST, creatinine, hemoglobin A1c, and thyroid hormones): SVs 2, 3, 4, 5
 - Additional serum will be obtained at all sites and stored at a central location (SCRI Seattle) for future use (3 ml in case anti-exenatide antibodies will need to be assessed)
- CEA: SVs 3, 4, 5
- Calcitonin: SV 5
- MRI (if needed): SV 1

Weekly Contact: Research participants will be contacted weekly by telephone/email to assess for potential adverse events, concomitant medications, and compliance with dosing. Participants will also be reminded about their urine collections, diet recalls, and return of the accelerometer during these phone calls.

Visit Schedule:

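### The only sensitivity analysis named for dropout is a completer analysis, which cannot test dropout that depends on unobserved week-36 BMI

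*Combined protocol and SAP*

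**What the plan says.** All references are to the combined protocol and SAP.

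- **Section 4, Analysis.** The primary analyses are intention-to-treat: "subjects will be analyzed according to their randomized assignment regardless of treatment received". The one analysis labelled as a sensitivity analysis follows: "data of all completers will be analyzed separately as a sensitivity analysis". Whether a completer is someone who reaches week 36 or week 54 is not defined. On incomplete follow-up the section says "Statistical methods have been selected to allow for inclusion of partial data", without naming a missing-data assumption.
- **Section 4, Aim 1, primary outcome analysis.** % change in BMI to week 36 is analysed with a piecewise linear mixed-effects model. "This model is a generalization of analysis of covariance (ANCOVA) that allows all follow-up repeated measures to be included".
- **Section 4, Aim 1, sample size and power.** The calculation assumes "a dropout rate of up to 20%, a sample size of 24 subjects per group (19 evaluable" after dropout).
- **Section 5, Subjects.** "We expect to screen 80 subjects to get 48 subjects enrolled and 38 to complete the study".
- **Section 6, Study Visits.** On withdrawal, "subjects will be asked to complete SV4 study procedures, not including the DEXA scan". The text does not say whether this visit takes place at withdrawal or at week 36, or which study week its data are assigned to.

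The documents contain no delta-adjusted, tipping-point, reference-based or pattern-mixture analysis.

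**The concern.** A sensitivity analysis for missing data should change the assumption on which the primary analysis rests. A likelihood-based mixed model is valid if, given the observed data, missingness does not depend on the unseen values. A completer analysis does not relax that. It discards the partial data of those who leave and requires completers to be comparable between arms.

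This protocol gives a reason to doubt that comparability. Section 7 describes gastrointestinal events as the main limiting factor for this drug class, and section 6 allows subjects who do not tolerate their dose to be discontinued. Completion may therefore depend on treatment, and the completer comparison loses the protection of randomisation.

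If subjects on ExQW leave and their unseen week-36 BMI is worse than their earlier data predict, the mixed model and the completer analysis can agree with each other while both miss the effect in all randomised subjects. No planned analysis would show how far the week-36 conclusion depends on that.

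**Working it through.** **Inputs.** Two-sided alpha 0.05, 24 per group and 19 evaluable (section 4). 48 enrolled and 38 completing (section 5). Pilot effect -4.29 and SD 3.84 percentage points of % change in BMI, from 3-month data (section 4, Table 3).

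**The plan's own figures.** A two-sample t-test with 19 v 19 and an effect of 1 SD has power 0.851, matching the stated 85%. 19 / (1 - 0.20) = 23.75, rounded up to 24. (48 - 38) / 48 = 20.8%, or 5 of 24 per arm if losses are equal. -4.29 / 3.84 = -1.12. None of these is disputed.

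**Can the two planned analyses reveal dropout that depends on unseen values?** In a simulation, 24 per arm had a true effect of -1 SD before any shift, an assumed week 18-36 correlation of 0.7, and 5 per arm with week 36 missing. The missing ExQW values were made k SD worse than MAR predicts. The MAR estimate used week-18 values from everyone.

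| k | All randomised | Completers | MAR estimate |
|---|---|---|---|
| 0 | -1.00 | -1.00 | -1.00 |
| 1 | -0.81 | -1.01 | -1.01 |
| 2 | -0.59 | -1.01 | -1.01 |

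The two planned analyses stay together while the all-randomised effect moves by about (5/24)k.

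**How large must the departure be to matter?** Hold the standard error at its 19 v 19 value: SE = sqrt(2/19) = 0.324 SD. With 36 df the critical t is 2.028, so the significance threshold is 2.028 x 0.324 = 0.66 SD, or 0.66 x 3.84 = 2.5 points. If the ExQW dropouts are delta SD worse than predicted, and placebo dropouts are left as predicted, the effect shrinks by (5/24) x delta. The tipping value is delta = (|observed effect| - 0.658) / (5/24). Full return of the ExQW dropouts to control level multiplies the effect by 19/24.

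| Observed effect (SD) | Tipping delta (SD) | In points (x 3.84) | Effect after full return | t (critical 2.028) |
|---|---|---|---|---|
| -1.12 | 2.22 | 8.5 | -0.89 | 2.73 |
| -1.0 | 1.64 | 6.3 | -0.79 | 2.44 |
| -0.8 | 0.68 | 2.6 | -0.63 | 1.95 |
| -0.7 | 0.20 | 0.8 | -0.55 | 1.71 |

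**An illustrative contrast.** Suppose 20% of ExQW subjects have missing week-36 data and have fully returned to control level. The all-randomised effect is 0.8 x -4.29 = -3.43 points, and -3.43 / 3.84 = -0.89 SD. A completer estimate would still be -4.29, larger by 4.29 / 3.43 - 1 = 25%. At 10%, 0.9 x -4.29 = -3.86, and the excess is 11%.

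**The case against.** The strongest reply is that the mixed model already does much of the work. BMI is measured at week 18, and dropout driven by an observed poor response at week 18 is MAR. In a simulation with 20% ExQW dropout driven by week-18 BMI, a true ExQW mean of -4.29, and assumed week 18-36 correlations of 0.5, 0.7 and 0.9, the completer mean was -4.67, -4.83 and -4.98. The MAR estimate stayed at -4.29 to -4.30. The two analyses diverge there, so the completer analysis does carry information. This stands. A reader might infer that both analyses go wrong together whenever non-responders leave. That holds only for dropout that depends on values not yet observed.

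Three further points also stand.

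- Stopping the drug is not the same as missing data. Under intention-to-treat, a subject who stops injections but stays in follow-up contributes an observed week-36 BMI.
- Five losses per arm is a ceiling. The protocol writes up to 20%, and section 5 ties the 38 to completing the whole study, including the open-label extension. Loss by week 36 may be smaller.
- The SV4 request at withdrawal reduces missing data. A reader might infer that these visits will be coded as week 36, but the text gives neither timing nor coding, so this needs only a clarifying sentence.

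Placebo dropouts could also depart from prediction and move the estimate the other way. None of this gives the plan an analysis that varies the MAR assumption.

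**Conclusion.** The gap is real and moderate in weight. The plan names one sensitivity analysis, and it rests on a stronger assumption than the model it accompanies. It can flag dropouts who differ on observed data, but its agreement with the primary result says nothing about dropout related to unseen week-36 BMI.

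How much that matters depends on the observed effect. At the planned effect of 1 SD the conclusion is robust: the tipping value of 6.3 points exceeds full loss of the benefit (3.84 points) among ExQW dropouts. At -0.8 SD, full return to control would be enough to lose significance, and at -0.7 SD a departure of 0.8 points would. A reader might therefore conclude that the week-36 result is fragile as designed. The figures do not support that; they show fragility only if the observed effect is smaller than planned.

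Nor is the 25% (or 11%) a bias in the primary analysis. It contrasts a completer estimate with one extreme assumption about subjects with missing data, using a 3-month pilot effect.

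The illustration assumes 5 of 24 missing per arm, a fixed SE, the pilot SD of 3.84, and a departure in the ExQW arm only.

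**What to change.** In section 4, Analysis, state the missing-data assumption of the mixed model. Replace the completer analysis as the named sensitivity analysis with one pre-specified delta-adjusted (tipping-point) analysis of week-36 % change in BMI in all randomised subjects. Vary delta for subjects with missing week-36 data over a stated range, and report the value at which the conclusion changes. A control-based imputation is an optional addition; one delta analysis closes the gap.

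Keep the completer result as descriptive, and define completer as week 36 or week 54. State that BMI from an SV4 visit made at withdrawal is analysed at its actual study week.

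The cost is SAP wording and some programming, with no new data. The sensitivity result may be less favourable than the primary one. The change should be made before unblinding, since a tipping-point analysis chosen afterwards is less credible.
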